In this study, we will test the effectiveness of two versions of a web-based tool to help people choose among Part D plans (Treatments A and B) relative to each other and relative to standard care (Control). Both treatment arms will incorporate simplified design and automated importation of an individual's drugs relative to standard care. The treatment arms will vary based on whether they provide expert guidance on recommended plans. In the control arm, study participants will be directed to the existing, publicly available Medicare.gov website and will receive instructions on how to download their drugs from the Palo Alto Medical Foundation (PAMF) patient-facing EMR (myhealthonline). Our study sample will include PAMF patients who were enrolled in Part D plans during the 2016 enrollment period. Prior to the 2017 open enrollment period (October 15 to December 7, 2016), we will invite a subset of PAMF patients enrolled in Part D plan to participate in a study examining the effectiveness of decision tools that provide personalized information on the financial implications of enrolling in different Part D plans.

For aims 1 and 2, the *primary study outcomes* will be:

- 1) Plan switching
- 2) Change in generosity of coverage of prescription drugs

- 3) Satisfaction with the choice process
- 4) Decisional conflict

Secondary study outcomes for aims 1 and 2

- 5) Enrollment in an expert-recommended plan
- 6) Difficulty choosing a plan
- 7) Confidence in choosing a plan
- 8) How much do you like the plan you chose
- 9) Satisfaction with chosen plan (people found this difficult)
- 10) Knowledge of the Medicare Part D prescription drug benefit?

For aim 3, we will analyze how the following patient characteristics influence enrollment in the trial and take-up of the treatment among those randomized to the treatment arm:

- 1) Prescription drug profile
- 2) Age
- 3) Use of myhealthonline

We will measure the primary study outcomes using a combination of administrative data and a post open enrollment survey administered to all study participants. We will also collect information on individual characteristics at the time of enrollment in the study and implement a survey examining use of the intervention tool to assess patient experience at the time of use.

D. Background

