The study has two types of interventions. The primary intervention is access to a decision tool (Aim 1) and the second is access to a decision tool with expert recommendations (Aim 2). People who enroll in the study will be randomized to one of three arms – two treatment and one control arm. People randomized to the treatment arms will receive a one of two versions of an on-line decision tool that automatically imports information on their prescription drug use from an electronic medical record into a decision tool developed as part of the study. In Treatment Arm A (expert recommendations), the tool will provide people with a score for each plan using an algorithm for generating expert recommendations based on the individual’s prescription drug usage and the characteristics of the different plans. In Treatment Arm B (individual analysis), we will provide information on each of the characteristics underlying the expert recommendation but not the recommendation itself. In the control arm, people will receive information on how to download their prescription drug information from the electronic medical record and how to access the Medicare.gov Plan Finder tool.

The calculations underlying the calculator as well as the expert recommendations will be powered by software we have purchased from a private third party, [REDACTED]. [REDACTED] produces software that allows a user to enter electronically a set of prescription drugs and returns information on associated out-of-pocket spending and the premium for each Part D plan available to the beneficiary. [REDACTED] also provides a “score” which represents a weighted average of the person’s estimated out-of-pocket spending and premium and the plan’s consumer satisfaction rating. Our user interface will, in turn, present this information to study participants in a patient-centered way and will manipulate the information in the two study arms as described above.

Participants will not actually enroll through our calculator. Instead we will direct participants to the appropriate company website or to the Medicare website where they can enroll.

The decision tool will be available throughout the open enrollment period.

K. Assessments

The study outcomes will be based on both primary data collection and administrative data sources. The sample size was chosen to adequately power the primary study outcomes.

Table 2: Summary of Outcome Measures for Comparative Effectiveness Evaluation

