Note: Primary study outcomes are italicized and bold.

Outcome Type		Measures	Data Source
Patient Satisfaction	Aims 1 and 2	• Satisfaction with choice process	Post-enrollment survey (primary)
Plan Choice	Aims 1 and 2	• Change in Part D plan chosen	2016 plan from enrollment app and 2017 plan from post

			open enrollment survey. Also question in post enrollment survey about “did they change their plan?”
	Aims 1, and 2	
 • Indicator of enrollment in lowest cost plan* • Indicator of enrollment in expert chosen plan* 	2017 plan from post open enrollment survey and information on OOP cost from [REDACTED] collected in admin panel.
Spending on prescription drugs	Aims 1, and 2.	
 • Difference in spending between lowest cost plan and chosen plan* 	[REDACTED] information for all plans and indicator of which plan was chosen from post open enrollment survey.
	Aims 1 and 2	
 • Difference in spending between 2016 plan and 2017 plan based on initial drug list.* 
Note: this address whether they switched to a lower cost plan
	[REDACTED] information for all plans and indicator of which plan was chosen from post open enrollment survey and which plan they were initially enrolled in from enrollment app.
Choice Experience	Aims 1 and 2	
 • Decisional Conflict • Knowledge about Part D program • Sources of information used • Time spent making decision 	Post-enrollment survey
		
 • How satisfied were you with the process of choosing a plan? • Decision confidence • Decision conflict • Choice knowledge – understanding of features of chosen plan • Right amount of information • Define user monitoring outcomes 	Intervention survey

* Note that calculating these variables requires a drug list for each person. For all people, we can construct an initial drug list based on the data in the EMR. For a subset of people who we observe using the tool, we can construct a revised drug list based on their activity in the tool. All these outcomes are based on the initial drug list.

L. Data Management

See data flow chart document.

M. Study Timeline

May 31 – Large dataset of test data

June 30 – UI changes implemented

July 15 – refreshed study data available to developer

July 31 – administrative console implemented

August 1 – Invitations mailed to participant

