August 1 – October 14 – recruitment and enrollment

August 1 – website available with “coming soon” information

August 1-August 30 – complete testing and list of changes to developer

September 30 – all changes implemented

October 1 – generate dataset of all [REDACTED] information for everyone chosen for recruitment.

October 1 – October 12 – final verification of functionality

October 15 – e-mail reminder (exact date depends on when tool is refreshed with 2016 open enrollment information)

October 15 – December 7 – Open enrollment – tool available

December 8 – e-mail follow up survey

January 4 – e-mail reminder about survey

December 8 – January 15 – follow up survey open

January 16 – e-mail gift cards

2. Statistical Plan

Sample size calculations:

	Hypothesis						
Outcome	Relative to control, treatment groups will have:	Baseline rate	SD	Change	Power	N per group	Notes:

Plan switching	Higher rates of plan switching	13.6		8.704	80%	305	Kling et al find 28% of people in treatment group relative to 17% in control. Ketcham et al 2013 find relative high rates of switching among new enrollees - 33% between 2009 and 2010 and that switching rates increased over time. KFF (2103) finds 13.6 among all ages in PDP plans. Change is Kling effect of 65% change applied to KFF baseline rate.
Satisfaction with choice process	Greater satisfaction with the choice process	2.6	1.03	0.6	80%	50	Scale of 1-4 in preliminary study with 1 as very satisfied. Data represent means of medicare versus all vendus arms where medicare is the baseline.
Decisional conflict	Less decisional conflict						
Coverage	enrollment in plans that coverage current drugs more generously	368	286	74	80%	236	Based on Kling et al
Coverage (alternative)	Increase in coverage generosity from last years to this years plan	-129	588.42	-543	80%	20	Based on Fall 2015 Results

Analyses:

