For aims 1 and 2, we will compare outcomes between each treatment group and the control group, defining the study population as those who enroll in the study through the enrollment portal and are randomly assigned to a study arm. The main focus of our analyses will be the comparison of the Expert arm relative to the control arm. We will calculate differences in means and proportions using t-tests and chi-squared tests based on the type of study outcome. We will also test the expert arm relative to the treatment arm without expert recommendations to identify the independent effect of expert recommendations. We will develop unadjusted estimates of the treatment effect as well as estimates adjusting for individual characteristics from survey and administrative data.

For aim 3, we will analyze how individual characteristics affect whether people choose to participate in the trial (take up of our invitation to participate). The key study variables will include age, use of myhealthonline, and prescription drug profile.

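### Four unranked primary outcomes have no alpha, testing order, multiplicity rule or success criterion, and the primary coverage measure is not settled

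*Combined protocol and SAP*

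**What the plan says.** Section 1.C (Study Overview) lists four primary outcomes for Aims 1 and 2: plan switching, coverage generosity, satisfaction with the choice process, and decisional conflict. The numbers 1 to 4 are list labels, since the secondary outcomes carry on from 5. Section 1.K says of the design: "The sample size was chosen to adequately power the primary study outcomes".

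The Analyses part of Section 2 gives the method for all of them: "We will calculate differences in means and proportions using t-tests and chi-squared tests based on the type of study outcome". It ranks the arm comparisons: "The main focus of our analyses will be the comparison of the Expert arm relative to the control arm". It does not rank the outcomes. It also plans the other treatment arm against control, and the two treatment arms against each other. The sample size table in Section 2 gives 80% power for each filled row and no alpha or sidedness.

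On coverage, three places differ:
- Section 1.C makes the primary outcome "Change in generosity of coverage of prescription drugs".
- Table 2 carries the key "Note: Primary study outcomes are italicized and bold". It marks "Difference in spending between lowest cost plan and chosen plan" and leaves "Difference in spending between 2016 plan and 2017 plan based on initial drug list" unmarked.
- The sample size table has a coverage row (236 per group) and an alternative coverage row, described as "Increase in coverage generosity from last years to this years plan" (20 per group).

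**The concern.** With four separate tests and no rule linking them, nothing in the plan prevents the best of the four from being reported as a positive primary result for the expert tool. The open choice of coverage measure adds a further degree of freedom. A reader of the results could not tell a pre-specified confirmatory finding from one picked after the data were seen.

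**Working it through.** **1. Which alpha do the plan's own sample sizes imply?**

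Inputs, from the sample size table: switching 13.6% plus 8.704 points, so p1 = 0.136 and p2 = 0.22304; coverage difference 74, SD 286; alternative coverage 543, SD 588.42; satisfaction 0.6, SD 1.03; power 80% throughout.

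Switching, pooled-variance formula, p̄ = (0.136 + 0.22304)/2 = 0.17952:

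n = [z(1−α/2)·√(2p̄(1−p̄)) + z(0.80)·√(p1(1−p1) + p2(1−p2))]² / (p2 − p1)²

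At two-sided 0.05: [1.960 × 0.5428 + 0.8416 × 0.5393]² / 0.08704² = 304.02, so **305**, the plan's figure.

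The other rows use the two-sample t-test (noncentral t):

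| Row | Stated | Two-sided 0.05 | One-sided 0.05 | Two-sided 0.0125 |
|---|---|---|---|---|
| Switching | 305 | 305 | 240 | 433 |
| Coverage | 236 | 236 | 186 | 335 |
| Coverage (alternative) | 20 | 20 | 16 | 28 |
| Satisfaction | 50 | 48 | 38 | 68 |
| Decisional conflict | blank | – | – | – |

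Three of the four filled rows match unadjusted two-sided 0.05 exactly and the fourth is within 2. So each outcome was sized as if it were the only test.

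**2. Chance of at least one false positive, Expert vs Control only.**

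Conditions: each of four outcomes tested at two-sided 0.05, all four nulls true, any one significant result counted as success, and a common correlation ρ between test statistics oriented towards benefit. The documents give no correlation, so a range is shown.

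- ρ = 0, either direction: 1 − 0.95⁴ = 0.185. Favouring the tool only: 1 − 0.975⁴ = 0.096.
- ρ > 0, either direction, with c = 1.960: 1 − ∫[Φ((c − √ρ·t)/√(1−ρ)) − Φ((−c − √ρ·t)/√(1−ρ))]⁴ φ(t) dt. Dropping the second Φ gives the favourable direction only.

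| ρ | Favouring the tool (one test: 2.5%) | Either direction (one test: 5%) |
|---|---|---|
| 0 | 9.6% | 18.5% |
| 0.5 | 7.8% | 15.6% |
| 0.8 | 5.7% | 11.4% |
| 0.9 | 4.7% | 9.4% |

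**3. What would error control cost for switching at 305 per arm?**

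Power = Φ[(0.08704·√305 − z(1−α/2) × 0.5428)/0.5393].

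- α = 0.05: Φ(0.846) = 80.1%.
- α = 0.05/3 = 0.0167: Φ(0.409) = 65.9%.
- α = 0.05/4 = 0.0125: Φ(0.305) = 62.0%.

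Under Holm, 0.0125 would hardly ever bind on switching. On the plan's inputs satisfaction has a standardised effect of 0.6/1.03 = 0.583. At 305 per arm that gives an expected z of about 0.583 × √(305/2) = 7.2, so power at 0.0125 exceeds 99.99%. Satisfaction passes the first step, and switching then faces 0.0167 or looser.

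Simulating Holm (400,000 runs per setting; first coverage row; ρ of 0, 0.5 and 0.8) gives switching power of 70-76% when decisional conflict is assumed to have no effect, 50% power or 80% power. If it had 99% power, switching power would be about 78%. The alternative coverage row gives 71-78% under the first three assumptions and about 80% under the last.

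**The case against.** **No any-one-wins rule is written.** This is the strongest reply. The sample size table attaches a directional hypothesis to each outcome, and the aims list the outcomes separately, so four outcome-specific reports is a fair reading. If all four had to succeed, there would be no inflation. This stands as a limit on the numbers: they are conditional. It does not remove the gap, because the plan adopts none of these readings. Under the all-four reading, overall power could not be stated either, since the decisional conflict row is blank.

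**The either-direction rate overstates the harm.** Part of it comes from results where the tool does worse, which could not be claimed as success. This is right, so the favourable-direction range leads here. Correlation may also be well above zero: switching and change in coverage both depend on the 2016 and 2017 plans.

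**Multiplicity is already limited by the main focus on Expert vs Control.** This is true for contrasts and is respected above, since only that contrast is counted. It does not order the outcomes. Nor does the fact that switching sets the sample size make it the sole primary outcome: Section 1.K speaks of the primary outcomes in the plural.

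**Holm is one choice among several and costs power.** This stands. A fixed sequence starting with switching is equally valid and keeps its 80%.

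**The coverage mismatch rests partly on typography.** Table 2's key refers to italics and bold, and the text as read shows only italics. The other three italicised measures do match Section 1.C, and the two coverage rows in the sample size table do not depend on formatting.

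**Conclusion.** The omission is real and should be corrected before outcome data are analysed. If any one significant primary outcome counts as success, the false-positive chance favouring the tool for Expert vs Control is about 5-10% (correlations 0.9 to 0) against 2.5% for a single test. In either direction it is 9-19% against 5%. These figures rest on an inferred two-sided 0.05, all four nulls true, and assumed equal correlations. The coverage definition is a separate inconsistency that does not enter these rates.

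Two stronger readings are not supported. A reader might infer that the trial, as planned, has a type I error of up to 19%. The documents do not say that one success suffices, and that figure includes results against the tool. A reader might also infer that Holm would cut switching power to 62%. That is the power at 0.0125, a step that the plan's own satisfaction inputs make switching very unlikely to face. About 66% at 0.0167, and roughly 70-76% overall, is the better description.

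**What to change.** In the SAP:

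1. State a two-sided alpha of 0.05.
2. Name the confirmatory contrast. Expert vs Control follows from the main focus in the Analyses section, but Section 1.J describes access to the tool itself (Aim 1) as the primary intervention and the expert version as the second. The two statements should be reconciled. Then control error across the four primary outcomes by Holm, or by a fixed sequence starting with plan switching if the sponsor wants to keep 80% power for switching at 305 per arm.
3. Name one primary coverage measure and align Section 1.C, Table 2 and the sample size table to it before outcome data are analysed.
4. Give the other two contrasts a stated place: tested in order after the confirmatory contrast, or reported with 95% confidence intervals.
5. If Holm is chosen, say that 80% switching power is for a single unadjusted test. On the plan's inputs it is about 66% at 0.0167 and roughly 70-76% overall, depending on the decisional conflict effect that the plan leaves blank. Do not print 62% as the power under Holm.

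Cost: SAP wording and a few sponsor decisions, with no added participants or data. The price is a stricter threshold and lower stated switching power under Holm. Under a fixed sequence, later outcomes can be tested only if earlier ones succeed.

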1. Eligibility verification - When patients log into the application, they will verify their name and address as well as their eligibility to participate in the study based on age, part d enrollment, and single representative from their household. (We will not exclude people from accessing the tool based on the single representative but will exclude them from data analysis). They will also identify the Part D plan in which they are currently enrolled.
2. Informed consent
3. Collect contact information - Consented participants will provide their e-mail address, using double-entry verification, and will be informed that further communication regarding the study will be by e-mail rather than by mail.
4. Pre-enrollment survey (Survey 1) - We will ask a few questions intended to provide information on individual characteristics of interest for the purpose of data analysis.

We will consider people who consent through the enrollment app as the “enrolled” population. The enrolled population will be randomly assigned to one of three arms (Treatment A, Treatment B or Control). Within 2 days after subjects enroll, we will send them by e-mail a letter that includes their study ID and information on how to access the tool, including the location of the website, when it will be available and log-in instructions. They will use the study ID to log into the website when open

enrollment begins. Shortly before and close to the end of open enrollment, we will send them another reminder with the same information.

We will provide support to study participants in the form of an e-mail address and a phone number they can call. This information will be available in our study tool, the control arm screen and the consent form. We will indicate that they will receive a response within 48 business hours.

Table 1: Recruitment Objectives

Sample Name	Category	Assumptions	Number of Study Subjects
Eligible for Recruitment	Eligible for recruitment		38,866
Recruited Sample	Chosen for mail recruitment	Derived from assumptions below	10,417
	Check for Eligibility	20% of those who contacted by mail check their eligibility	2,083
Enrolled Population	Enroll in Study	Assume 40% attrition among those who access enrollment app	1,250
Study Sample	Complete final survey	Assume 80% of those enrolling complete final survey	1,000
Objective based on sample size calculation		based on 3 arms of 305 each	915

Source: trial protocol tables google sheet – recruitment objectives

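### The primary spending gap has no prespecified baseline covariate and no named primary estimate, so the main contrast accepts imprecision it could avoid at no cost

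*Combined protocol and SAP*

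**What the plan says.** **Outcome.** Table 2 (Protocol, section K) marks this spending measure as primary: "Difference in spending between lowest cost plan and chosen plan". It is a follow-up level, priced on the initial drug list. The Study Overview (section C) instead lists a change in how generously drugs are covered, which already involves the 2016 plan. The sample size table carries a row for each version. One has the hypothesis "enrollment in plans that coverage current drugs more generously" and the figures "368 286 74 80% 236". The alternative row concerns the change from last year's plan, with the figures "129 588.42 -543 80% 20" (its mean also carries a minus sign).

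**Analysis.** Section 2, Analyses: "We will calculate differences in means and proportions using t-tests and chi-squared tests based on the type of study outcome". The same paragraph makes Expert versus Control the main contrast. It adds that unadjusted estimates will be accompanied by "estimates adjusting for individual characteristics from survey and administrative data". It lists no covariates for aims 1 and 2 and does not rank the two sets of estimates.

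**Baseline ingredients.**
- The 2016 plan is recorded in the enrollment portal (section G, function 1), before consent and assignment: "They will also identify the Part D plan in which they are currently enrolled".
- The drug list is covered by the note to Table 2: "For all people, we can construct an initial drug list based on the data in the EMR".
- Vendor cost information for all plans is an input to Table 2. The timeline (section M) has it generated on October 1 for everyone chosen for recruitment.

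**The concern.** The baseline counterpart of the outcome is the cost of staying in the 2016 plan minus the cost of the lowest-cost plan, on the same drug list. It does not depend on arm. On the plan's own switching figures most people keep their plan, so the follow-up gap should follow the baseline gap for most of the sample. An unadjusted t-test leaves that predictable person-to-person variation in the error term.

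The reference to individual characteristics permits this covariate but does not commit to it. It also leaves both the covariates and the headline estimate open until the data have been seen. At stake are the width of the Expert versus Control interval on a primary outcome and the clarity of which estimate carries the conclusion.

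**Working it through.** **Step 1: reproduce the plan's figure.** Inputs from the sample size table: difference 74, SD 286, power 80%. No alpha is stated; two-sided 5% is assumed.

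n per arm = 2 × SD² × (1.960 + 0.842)² / difference² = 2 × 81,796 × 7.849 / 5,476 = 234.5, so 235. The noncentral t version gives 235.4, so 236, as stated. One-sided 5% would give 185. No baseline term enters the stated figure.

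**Step 2: the unadjusted test at the planned size.** SE = 286 × √(2/305) = 23.16. For $74, 74/23.16 − 1.960 = 1.235, which is 89.2% power. At the expected 333 per arm it is 91.6%. The detectable difference at 305 per arm and 80% power is 2.802 × 23.16 = $64.9.

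**Step 3: adjust for the baseline gap.** With baseline-outcome correlation r, residual SD = 286 × √(1 − r²), and the share of variance removed is r². The documents do not give r, so it is shown as a range.

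| r | Variance removed | Residual SD | N per arm for $74 | Detectable at 305 | Power for $74 at 305 |
|---|---|---|---|---|---|
| 0 | 0% | 286 | 235 | $64.9 | 89.2% |
| 0.3 | 9% | 273 | 214 | $61.9 | 91.8% |
| 0.5 | 25% | 248 | 176 | $56.2 | 95.8% |
| 0.7 | 49% | 204 | 120 | $46.3 | 99.4% |
| 0.8 | 64% | 172 | 85 | $38.9 | >99.9% |

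The N column uses the normal approximation. The dollar figures take 286 as the SD of the outcome itself.

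**Step 4: what r might be.** The switching row gives 13.6% in control and 13.6 + 8.704 = 22.3% under treatment, so 86.4% and 77.7% stay.
- *Favourable case.* Stayers' gaps carry over unchanged, and switchers' new gaps come from the same distribution, unrelated to the old ones. Then r equals the share who stay: 0.864 (r² = 75%) and 0.777 (r² = 60%). The average of the two arms is 0.82, r² = 67%; simulation gives about 68%.
- *Price drift.* If stayers' own correlation is only 0.4 to 0.8, r runs from 0.4 × 0.777 = 0.31 to 0.8 × 0.864 = 0.69, so about 10% to 48% is removed.
- *Switching more likely when the gap is larger.* With switching proportional to the gap, simulation gives a reduction of 13% to 42%, depending on drift and on where switchers land.

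**Step 5: can the plan's own SDs supply r?** No. If the level has SD 286 at both times, a change score cannot have an SD above 2 × 286 = 572, yet the alternative row gives 588.42. The two rows must rest on different populations or measures. The alternative row's N of 20 does reproduce if 543 is read as the between-arm difference (19 by normal approximation; 19.4, so 20, by noncentral t).

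**The case against.** **Adjusted estimates are already planned.** True, and a reader who infers that the plan omits adjustment would be wrong. What is missing is the covariate list and the ranking of the estimates.

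**The test already has power.** This stands for the stated $74; a reader might infer an underpowered comparison, and the documents do not support that. The trial is sized on switching, and 305 exceeds the 236 needed here. Precision still matters if the effect is smaller. As an illustration that is not the plan's target, if the extra 8.704 points of switchers each removed an average gap of $368, the difference would be 0.08704 × 368 = $32. Power at 305 per arm would be 28% unadjusted and 49% at r = 0.7.

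**Chance imbalance in baseline gaps.** A reader might take this as bias. It is not: under random assignment the t-test's standard error already allows for it. Adjustment narrows the interval; it does not repair an invalid test.

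**The Study Overview's outcome is a change, and Table 2 also has a 2016-to-2017 difference.** This is the strongest point. If the change measure is primary, the baseline is already in the outcome. If both years' plans are priced on one file, the lowest-cost term cancels, and the follow-up gap minus the baseline gap is exactly that Table 2 row. When switching is unrelated to the gap, a plain t-test on the change recovers nearly all of the gain. That does not carry over when switching rises with the gap. In simulations of that pattern the change score cut variance by about 6% or less, or raised it, while adjustment cut it by 13% to 42%. The change score does better if switchers land on plans no cheaper on average, so the size of this contrast depends on the assumption. With equal variances at both times, the adjusted analysis has (1 + r)/2 of the change-score variance, which is 10% to 25% less at r = 0.8 to 0.5.

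**Conclusion.** The point holds as a prespecification and efficiency issue. The plan neither names the baseline gap as a covariate nor says which estimate is primary, and its documents disagree on which spending measure is primary. The cost is a wider interval than the collected data allow: roughly 13% to 68% of the treatment-effect variance under the patterns simulated, and nearer 10% if stayers' gaps drift strongly. A reader might infer that most of the precision is certainly lost. The documents do not support that, because the upper figures need stable prices and switching unrelated to the gap.

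The result rests on two-sided 5% testing without multiplicity adjustment, equal SDs across arms, a linear baseline relation, a gamma-shaped gap with mean 368 and SD 286 in the simulations, and the plan's assumed switching rates. The t-test remains valid and meets its stated target.

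**What to change.** 1. Reconcile the Study Overview with Table 2 on which spending measure is primary.
2. State in Section 2, Analyses, that its primary analysis is a linear model with arm and the baseline gap, with robust standard errors. Define the baseline gap as 2016-plan cost minus lowest-cost-plan cost, on the same initial drug list and the same vendor plan file where the 2016 plan is still offered. Say how it is priced where that plan is no longer offered.
3. Keep the unadjusted t-test as a sensitivity analysis.
4. If the 2016-to-2017 difference becomes primary, use the same covariate. Where the lowest-cost term cancels, the adjusted arm effect is the same for either measure, apart from sign convention.

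The cost is a few sentences of analysis-plan text and one derived variable. No extra participants or data collection are needed.
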